Participants who make any response other than "not at all" on the suicidal ideation question of the Prime MD (Question 1i), indicate suicidal ideation, have attempted suicide in the past month, or have had a suicide attempted in the past 5 years on the MlNI suicide subscale will not be eligible to participate in the study. If the participant has attempted suicide between 6-10 years ago, then the LMM must approve eligibility. To determine if a participant is in immediate danger, staff will ask the participant two questions to determine level of risk: "Are you feeling suicidal?" and "Do you have a plan to kill yourself today?" If the participant has a plan to kill himself/herself, staff will put the participant in contact with the suicide prevention hotline (Durham Center Crisis Line at [name]; Philadelphia Suicide Prevention [contact] or UPenn's HELP line: [name]). If the participant refuses to talk to the hotline and leaves, the study staff will call 911. They will also contact the Study Coordinator and Site PI to inform them of the situation as soon as possible. If the participant does not have a plan to kill himself/herself, the study staff will recommend he/she speaks with the suicide hotline. The visit will continue as normal, but the participant will not be eligible for the study. The participant will be paid \$30 and provided with local mental health resources. The on-site clinician will be available by phone for consultation within 24-hours.

Additionally, any participant whose score on the Prime MD indicates Major Depressive Disorder will be administered the Beck Depression Inventory (BDI) and the GAD 2 week monitoring on paper. The BDI will be submitted, along with the Prime MD, Brief Medical History Questionnaire, Brief Medical History Follow-up Questionnaire, and the MINI suicide subscale to the licensed medical monitor for eligibility review. If he/she determines a participant with Major Depressive Disorder is eligible for study participation, the participant will complete the BDI each visit to monitor changes in his/her mood.

21. Adverse Events (AE)

21.1. Identifying Adverse Events

While participating in the trial, adverse events and concomitant medications will be assessed at every study visit and vital signs and carbon monoxide will be measured. Adverse events will typically be identified during the administration of the Health Changes Questionnaire and Respiratory Health Questionnaire, and in some cases during the administration of the CESD. Other events may be identified from physiological study measures or by spontaneous reports during non-scheduled assessments. The medical monitor is notified about all AEs within 10 days.

Questionnaire items that will be reviewed:

- 1. Health Changes Questionnaire
 - 1. Have you had any negative changes in your physical or mental health since your last visit? If yes, briefly describe.
 - 2. Since your last visit, have you received any form of medical care? If yes, briefly describe.

No new AE report will be required if one or more conditions below are met and the description does not otherwise meet the definition of an AE.

- a. Existing AE already open for reported symptom
- b. Pre-existing condition without increase in severity or frequency of symptoms (brief medical history will be updated if not previously reported).
- c. Nicotine withdrawal symptoms that don't meet AE criteria
 - A. The following withdrawal symptoms are considered expected withdrawal symptoms and are not considered AEs
 - 1. Desire or craving to smoke
 - 2. Restlessness
 - 3. Impatience
 - 4. Increased appetite, hunger, weight gain*

*If a participant indicates any clinical behaviors such as binging or purging this should be recorded as an Adverse Event and the PrimeMD should be completed.

- B. The following withdrawal symptoms would be considered an AE if the participant indicated the symptom had a significant impact on your daily life, caused a major disruption of functioning, or took any medication for it.
 - 1. Anger, irritability, frustration
 - 2. Difficulty Concentrating
 - 3. Insomnia
 - 4. Nightmare/Night Terrors
 - 5. Depressed (sad) mood*
 - 6. Anxious (nervous) mood*

*If a depressed (sad) mood and an anxious (nervous) mood AE is reported, the participant will complete the Prime MD and be assessed for suicidality.

- d. Received preventative or follow-up medical care.
- e. Other (explain).
- 2. Respiratory Health Questionnaire: In the past week, have you experienced any health problems, such as cold, flu, or other respiratory illness that would affect these respiratory symptoms?

No new AE report will be required if one or more conditions below are met and the description does not otherwise meet the definition of an AE.

- a. Existing AE already open for reported symptom
- b. Pre-existing condition without increase in severity or frequency of symptoms (brief medical history will be updated if not previously reported; e.g., seasonal allergies).
- 3. CESD: If the participant **scores 16 or higher and is not already being monitored for depression**, a 'Adverse Event Form' should be completed and the LMM will provide information regarding follow-up. If there is already an open event, information will be added to the existing 'Adverse Event Form.'

Physiological data that will be reviewed:

- 1. CO level: The 'Adverse Event Form' should be completed if the average CO within a visit is:
 - o CO is greater than 50 ppm if CO at Baseline is < 20 ppm.
 - CO is greater than 60 ppm if CO at Baseline is 20 34 ppm.
 - o CO is greater than 70 ppm if CO at Baseline is 35 49 ppm.
 - CO is greater than 80 ppm if CO at Baseline is 50 64 ppm.
 - CO is greater than 90 ppm if CO at Baseline is 65 80 ppm.

2. Blood Pressure:

- The 'Adverse Event Form' and 'Blood Pressure and Heart Rate Symptom Checklist' should be completed if an automatic and subsequent manual blood pressure measurement during the same visit is at or above 160 SBP or 100 DBP.
- The 'Adverse Event Form' and 'Blood Pressure and Heart Rate Symptom Checklist' should be completed if an automatic and subsequent manual blood pressure measurement during the same visit is below 90 SBP or 50 DBP.

3. Heart Rate:

- The 'Adverse Event Form' and 'Blood Pressure and Heart Rate Symptom Checklist' should be completed if an automatic and subsequent manual heart rate measurement during the same visit is at or above 105 bpm.
- The 'Adverse Event Form' and 'Blood Pressure and Heart Rate Symptom Checklist' should be completed if an automatic and subsequent manual heart rate measurement during the same visit is below 45 bpm.

22. Management of SAEs and Other Study Risks

The site medical monitor(s) will review all AEs. A study participant may be discontinued from the study if the medical monitor and/or PI determine it is the best decision in order to protect the safety of a participant. In the event that a participant either withdraws from the study or the investigator decides to discontinue a participant due to an AE/SAE, the participant will have appropriate follow-up medical monitoring. The participant experiencing an AE/SAE will be followed until the problem resolves, stabilizes, or is clearly unrelated to the study cigarettes. Any AE that remains open will be reviewed and closed at the 30 day follow-up visit.

23. Reporting of SAEs to the IRB, FDA, and NIDA

Serious adverse events (SAEs) as defined in 21 CFR 312.32 (death, life-threatening, hospitalization (initial or prolonged), disability or permanent damage, congenital anomaly/birth defect, required intervention to prevent permanent impairment or damage (devices), other serious (important medical outcomes)) that are related or possibly related to study participation will be reported to the Administrative Core, all site IRBs, the NIDA Scientific Officer ([name]), the NIDA Project Officer ([name]), FDA, and the Data Safety and

Monitoring Board. All Site IRBs require that fatalities related to the study be reported within 24 hours, that all other SAEs be reported within 5 business days. Reports of all SAEs will also be documented within NIDA's SAE data monitoring system, or SAETRS, within 72 hours.

24. Reporting of IRB Actions to NIDA

Actions taken by the local IRBs in response to SAEs will be reported to NIDA in the annual noncompetitive continuation application, as will reports of changes or amendments to the protocol as a result of an SAE. Recommendation for trial discontinuation, for significant changes or amendments to the protocol, or other significant findings as a result of an SAE will be reported immediately to the NIDA Scientific Officer ([name]) and Project Officer ([name]) by the Project PI.

25. Reporting Changes or Amendments to the Protocol

Any changes or amendments to the protocol made in response to adverse events/SAEs will be discussed with [name] and [name], and then requested in writing to the IRB, which will then grant or deny permission to make the requested change in protocol. The DSMB and FDA will be notified about any significant changes to the protocol. NIDA will be informed of any approved changes in protocol by documentation in the noncompetitive continuation application. Changes that significantly alter the scope of the research or the ability of the research to achieve its specific aims will be submitted to [name] and [name], the DSMB, FDA, and NIDA for approval prior to implementation.

26. Withdrawal or Monitoring of Participants

For the participant's protection, participants will be withdrawn immediately from the study if any of the following occur:

- Cardiovascular disease (CVD) event: Typically includes MI (heart attack), PTCA (angioplasty/stenting), bypass surgery, stroke, peripheral vascular disease (arterial blockages in arms or legs leading to procedure or surgery). Less common CVD problems would be new cardiac arrhythmias (e.g., new atrial fibrillation) or new valvular disease (e.g., mitral or aortic regurgitation).
- 2. DVT/PE (deep vein thrombosis/pulmonary embolism, i.e., blood clots in the venous system).
- 3. Suicide Attempt: A participant will be withdrawn if he/she attempts suicide at any time during participation in the study.
- 4. Psychiatric Hospitalization: A participant will be withdrawn if he/she is hospitalized for psychiatric reasons at any time during participation in the study.
- 5. Pregnancy: If participant indicates she is pregnant or has a positive pregnancy test at the Randomization Visit, she will be withdrawn from the study, and this event will remain open until delivery. At that time the licensed medical monitor will contact the participant to ask a

few questions about the baby's health and will update the open 'Adverse Event Form'. A positive pregnancy test at follow-up will trigger an 'Adverse Event Form' to be completed but will not result in withdrawal since she is no longer receiving study product.

6. Expired breath carbon monoxide increase: A participant will be withdrawn from the study if their CO reading is 100 ppm or greater.

The following will be monitored and can lead to the participant being withdrawn by the Pl or Licensed Medical Monitor:

- Blood pressure (BP) or heart rate (HR) changes: If any of the following occur post-enrollment:
 BP is at or above 160 SBP or 100 DBP, 2) BP is below 90 SBP or 50 DBP 3) HR is at or above 105 bpm, 4) or below 45 bpm.
- 2. Changes in tobacco product use: if during the weekly visits, participants self-report a greater than 100% increase in cigarette per day (total cigarettes, including study and non-study cigarettes) relative to baseline, or a 50% increase in cigarettes per day relative to baseline that is accompanied by an average daily use of 2 ml e-liquid or more."
- 3. Expired breath Carbon Monoxide increase: An 'Adverse Event Form' will be documented and the participant will be monitored by the medical monitor if CO exceeding the following criteria based on Baseline CO:
 - a. CO is greater than 50 ppm if CO at Baseline is < 20 ppm.
 - b. CO is greater than 60 ppm if CO at Baseline is 20 34 ppm.
 - c. CO is greater than 70 ppm if CO at Baseline is 35 49 ppm.
 - d. CO is greater than 80 ppm if CO at Baseline is 50 64 ppm.
 - e. CO is greater than 90 ppm if CO at Baseline is 65 80 ppm.
- 4. Medication changes: If a participant begins taking any of the exclusionary medications or other medications that could potentially have a smoking-drug interaction post- enrollment, the licensed medical monitor will determine how best to monitor and minimize potential risks (including withdrawal if warranted). We will also recommend that a letter be sent to the participant's physician (with their consent), making them aware of the potential changes in smoking that could occur as a result of participation in the study.
- 5. Any hospitalization or debilitation in which participation in the study could be detrimental to the recovery process. This will be self-reported by the participant and will be reviewed by the site PI and medical monitor to determine whether continued participation in the study is appropriate.
- 6. If a participant is behaving in an inappropriate or threatening manner, admits to lying about eligibility criteria, including omitting previous medical diagnoses and medications, is participating in other smoking research studies that could affect the primary outcome measures, does not follow study instructions, etc., then the PI can withdraw him/her from the study at the PI's discretion.
- 7. If a participant fails to attend his/her Randomization Visit within the 21-day allowable visit window, he/she will not be eligible to reschedule this visit or continue participation in the study.
- 8. If there is reason to believe the participant is sharing the study product with other people.

If a participant chooses to withdraw from the study at any time, we will them to return to the lab to return study product and equipment and to receive their final study payment. We will also ask participants who have been randomized if they would like to complete the end of study questionnaires.

27. Investigational Tobacco Product

The Co-Directors of this Center grant, Drs. [name] and [name], have submitted an Investigational Tobacco Product (ITP) application to the FDA to cover the experimental cigarettes being used in this study.

28. Study Endpoints / Outcomes

28.1. Primary Endpoints:

• Total number of cigarettes smoked per day (i.e. study plus non-study cigarettes) as measured by daily Interactive Voice Response (IVR) phone calls. The total number of cigarettes smoked per day will be averaged using the last 7 days prior to the Week 12 visit. We note that subjects have the opportunity to correct data entry errors in MR from calls made since the last visit at each visit (for example, if a subject entered 100 cigarettes instead of 10 cigarettes). In these cases, the original IVR data will be replaced with the corrected data to create a final, cleaned version that will be used for analysis (herein called "IVR-Revised"). A secondary, repeated measures analysis will also be completed using the mean of the total number of cigarettes smoked per day at each visit, calculated using IVR calls from the previous 7 days. In the event that two visits were less than 7 days apart, then the average will be calculated using only days since the last visit.

28.2. Secondary Outcomes:

- Cigarette smoke exposure: mercapturic acid CEMA
- Smoke-free days: the number of days not smoking any combustible products based on IVR-Revised

28.3. Exploratory Outcomes:

- Cigarette characteristics: CES subscale score for Satisfaction
- Discomfort/dysfunction: MNWS total
- Vaping device use: number of days using assigned vaping device (IVR)
- Study cigarettes per day (CPD): the mean cigarettes smoked per day based on 7 days' Daily Interactive Voice Response (IVR)-Revised data before the week 12 visit.
- Cigarette dependence: Total scores on the FTND

- Compliance/retention: Non-study cigarette use (IVR), urinary anatabine, drop-out rate
- Nicotine exposure: urinary total nicotine equivalents
- Cigarette smoke exposure: breathe CO, urinary mercapturic acids, puff topography
- Relative reinforcement: Preference Task, Purchase Task
- Cigarette dependence: WISDM Primary Subscales, Penn State Smoking Questionnaire, and PATH Smoking Dependence questions
- E-cigarette dependence: Penn State E-cigarette questionnaire, PATH Vaping Dependence questions
- Hypothetical cigarette and vaping device use: Purchase Task, Predicted Behavior Questionnaire
- Discomfort/dysfunction: urge to use questionnaire, CES-D total score
- Vaping device use: intensity (puff/day) of use of the assigned vaping device (IVR), eliquid mls used per week; e-liquid flavor preferences
- Smoking/vaping context: Environmental and Social Influences on Tobacco Use, Context of Product Use
- Product expectancies: Vaping Utility Questionnaire, Smoking and Vaping Expectancies Questionnaires
- Perceived risk: Perceived Health Risk Questionnaire
- Other health-related behaviors: Breath alcohol, urine drug screen, Alcohol Use Questionnaire, Drug Use Questionnaire, weight
- Cigarette characteristics: CES subscale scores
- Intention to quit: Stages of Change, Contemplation Ladder, Quit Attempts
- Post-intervention changes in tobacco use behavior: 30-day tobacco use guestionnaire
- Qualitative Interview: Themes related to product use patterns, e-liquid flavor selection, non-compliance and general study feedback

28.4. Safety Outcomes:

- Potential adverse consequences: Change in mental (CES-D) or physical health (Respiratory and Global Health Questionnaire, Health Changes Questionnaire, weight)
- Measures of cardiovascular function: Heart rate, blood pressure
- Increased nicotine exposure as indicated by 100% increase in total nicotine equivalents relative to baseline or a 50% increase in cigarettes per day relative to baseline that is accompanied by an average daily use of 2ml e-liquid or more.
- Adverse events

29. Statistical Approach

This is a 2x2x2 factorial design in which participants will be randomized with equal probability to one of eight groups. Randomization will be stratified by age (18-24 vs. 25+) and menthol preference; a set number/percentage of either age and menthol vs. non-menthol preferring smokers will not be enforced. All analyses described below will follow the intent-to-treat principle (i.e. subjects will be analyzed according to their randomized treatment assignment regardless of their compliance) unless otherwise noted.

Our primary objective is to test the main effects of cigarette nicotine content, e-liquid nicotine content and e-liquid flavors, as well as the interactions among these factors. The primary endpoint will be total CPD (i.e. study plus non-study CPD) based on IVR-Revised. The primary analysis will compare CPD by factor at the week 12 visit using linear regression. Treatment groups should be balanced at baseline, and as a result our primary analysis will only adjust for baseline CPD, week and the three stratification factors (site, age, and menthol preference). This will be considered the "unadjusted model" for the purposes of this document. We will start with a model that includes all two-way interactions between the three factors (note: the three way interaction will not be considered). Two-way interactions that are not significant will be removed from the model and the final model will include the three factors, any two-way interactions significant at the 0.05 levels, baseline CPD, and the three stratification factors. The estimation and testing of main effects in the presence of significant interactions will be completed within levels of the other factor, otherwise, global estimates of the main effects will be obtained. Whenever possible, secondary endpoints will be analyzed following the approach to testing the main effects and interactions described above. Biomarkers of toxicant exposure are expected to be skewed and will be analyzed on the log scale. Likewise, exploratory endpoints will be analyzed following the approach outlined above using a linear mixed model or logistic regression, as appropriate, depending on the type of endpoint (continuous, binary). Finally, we will complete subgroup analyses following the approach described above within each subgroup (age: 18 - 24 vs. 25+; menthol preference; sex). We will not use formal multiple comparison adjustments for secondary endpoints because we have included only 2 outcomes that are likely correlated with each other and the primary endpoint. Likewise, we will not correct for multiple comparisons for our subgroup analyses as they are considered exploratory.

Study staff will make every effort to minimize missing data in the proposed clinical trial. The success of our previous and ongoing trials suggests that missing data will be minimal. Nevertheless, we plan to complete a sensitivity analysis to evaluate the impact of missing data on trial conclusions.

We will compare subjects with and without missing data in order to identify baseline covariates associated with missing data. Our primary approach to handling missing data will be multiple imputation where missing values are imputed using regression models developed from baseline covariates (Little and Rubin, 2002). Daily IVR data will be averaged within a week using complete observations (i.e. we will average the number of cigarettes smoked per day for complete calls). In our previous work ([name] et al., 2015), 90% of weeks had 0 or 1 missed call, while 4% of weeks were completely missing, which suggests that an alternate approach to handling sporadically missed calls will only impact a small number of weeks for the entire trial. Missing

weekly average IVR data (i.e. when all calls in a week are missing) will be analyzed using multiple imputation.

In addition, we will conduct a sensitivity analysis of the primary and secondary endpoints using baseline-carried-forward and last-observation carried forward. The results of these analyses will be compared to the primary analysis to evaluate the robustness of our conclusions.

For the qualitative data, we will use grounded theory to develop hypotheses related to the topics of interest. Interviews will be audio-recorded and transcribed verbatim. The interviews will be analyzed using open and axial coding. Themes will emerge during data analysis, which will be ongoing throughout the project.

30. Power Analysis

We will enroll 480 subjects (n=60/group) and assume 75% retention at week 12 (i.e. 360 completers) based on our current and previous trials. Power calculations are presented for testing the main effects and the interactions between cigarette nicotine content and e-cigarette nicotine concentration or flavor. Effect size estimates were based on our previous studies of VLNC cigarettes and the assumption that the main effect of e-liquid nicotine content and the interaction between e-liquid nicotine content and cigarette nicotine content will be similar to the effect of cigarette nicotine content. This assumption is supported by the results of [name] and Jones, who found that the effect of transdermal nicotine on use of VLNC cigarettes was as large as the main effect for cigarette nicotine content ([name] & Jones, 2009). The impact of flavors is largely unknown, therefore, we assumed an effect size similar to e-liquid nicotine content (A in table below) as well as one half as large (B in table below). All power calculations were completed assuming a type-I error rate of 0.05. Power calculations for the main effect were completed in PASS 13. Power for testing interactions was calculated by simulation and is consistent with the well-known theoretical relationship between the power for testing main effects and the power for testing interactions.

	Effect size		Pow	Power - Subgroups ^c								
	shown as	Main	Main			Main						
Outcome	Diff (SD)	Effect ^A	Effect ^B	Interaction ^A	Interaction ^B	Effect ^A	Interaction ^A					
			Primar	y Outcome								
CPD ¹	6.3 (7.2)	0.99	0.99	0.99	0.54	0.99	0.83					
Secondary Outcomes												
FTND ¹	1.31 (1.77)	0.97	0.94	0.94	0.41	0.94	0.69					

Log(CEMA) 1	0.51	0.96	0.73	0.73	0.25	0.74	0.44
	(0.92)						

^A Effect size for flavor equal to effect size for nicotine. ^B Effect size for flavor equal to half the effect size for nicotine.

31. Subject Identifier

The subject identifier is an alpha-numeric combination. Example: M-G001 would be Wake Forest University's first subject.

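### The footnote that triggers the Prime MD and suicidality assessment joins depressed and anxious mood with *and*, so it is unclear whether a depressed-mood adverse event alone is enough

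*Combined protocol and SAP*

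**What the plan says.** Section 21.1 (Identifying Adverse Events) sorts withdrawal symptoms reported on the Health Changes Questionnaire into two lists. List A symptoms are expected and are not AEs. A list B symptom becomes an AE if the participant indicates that "the symptom had a significant impact on your daily life, caused a major disruption of functioning, or took any medication for it". Two entries in list B are "5. Depressed (sad) mood" and "6. Anxious (nervous) mood". Each is followed by its own asterisk, and the shared footnote reads: "If a depressed (sad) mood and an anxious (nervous) mood AE is reported, the participant will complete the Prime MD and be assessed for suicidality".

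Other parts of the protocol bear on the same risk:

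- **AE handling.** Section 21.1 states: "The medical monitor is notified about all AEs within 10 days". Section 22 adds: "The site medical monitor(s) will review all AEs".
- **Health Changes Questionnaire.** Every visit after screening includes the question "Have you had any negative changes in your physical or mental health since your last visit".
- **CES-D.** It is taken at Visits 4, 8 and 12 (Section 6.4) and at early termination (Section 8.2). At a score of 16 or more in someone not already monitored for depression, an AE form "should be completed and the LMM will provide information regarding follow-up".
- **Prime MD and MINI suicide subscale.** Section 32 schedules both at screening only.

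**The concern.** The footnote is an operative safety instruction, and its conjunction decides who is assessed. With *and*, a participant who reports only depressed mood, severe enough to affect daily life, disrupt functioning or need medication, does not meet the condition. That participant would be assessed for suicidality at the discretion of staff or the monitor, not by rule.

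The Prime MD holds the suicidal ideation item (Section 20, Question 1i). Ideation in the past month is excluded at entry (Section 3.6, item 26), so ideation that arises later has to be picked up during the study. Section 17, item 11, names mood change as a possible result of changing nicotine use. With two sites recruiting (Section 3.1), the sentence could be applied in two ways.

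**Working it through.** No power, alpha or rate is involved. The check is whether the footnote has one meaning and, if not, whether another section supplies it.

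**Step 1: can a depressed-mood AE occur alone?** Yes. List B judges each symptom on its own impact, disruption or medication. Nothing ties depressed mood to anxious mood before the footnote.

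**Step 2: what does the footnote require?** The possible patterns of mood AE are:

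| Depressed-mood AE | Anxious-mood AE | Required under *and* | Required under *or* |
|---|---|---|---|
| yes | no | no | yes |
| no | yes | no | yes |
| yes | yes | yes | yes |

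The word settles the two single-mood rows. The table shows where the readings part. It does not say how often each row occurs.

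**Step 3: which reading does the layout support?** Separate list entries, an asterisk on each, and a singular AE with a singular verb all favour either one being enough. The conjunction favours both being needed.

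**Step 4: does another section resolve it?**

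- Section 20 is written around screening. Its consequences are ineligibility, the screening payment, and BDI monitoring for participants with Major Depressive Disorder whom the medical monitor admits. It does not say which mood AE during the study calls for a repeat Prime MD.
- Section 21.1 names one other Prime MD trigger, binging or purging, which carries no suicidality assessment.
- The CES-D rule leads to an AE form and monitor follow-up. It names neither the Prime MD nor a suicidality assessment.
- Sections 21.1 and 22 on notification and review specify no suicidality assessment.

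**Step 5: what does the schedule guarantee after screening?** Section 32 has 11 such visits: 91, 00, 01, 02, 03, 04, 06, 08, 10, 12 and 30.

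| Instrument | Post-screening visits scheduled |
|---|---|
| Prime MD | 0 of 11 |
| MINI suicide subscale | 0 of 11 |
| CES-D | 3 of 11 (04, 08, 12), plus early termination |
| BDI, GAD | 11 of 11, but only if needed |
| Health Changes Questionnaire | 11 of 11 |

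The CES-D is therefore not scheduled at 11 − 3 = 8 of these visits. The zero for the Prime MD does not favour either reading, because the instrument is event-driven under both. It does mean that the footnote is the only rule requiring a suicidality assessment for a mood AE once a participant is enrolled.

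**The case against.** The strongest reply is that the intended meaning is easy to recover. Someone recording only depressed mood is sent to the footnote by that item's own asterisk, and a both-required rule would be an odd thing to attach to each item separately. On this view it is a copy-edit.

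Oversight is also wider than the footnote. An isolated depressed-mood AE reaches a clinician under either reading. Section 22 requires follow-up until the problem resolves, stabilizes or is clearly unrelated to the study cigarettes, and allows discontinuation for safety. Participants with Major Depressive Disorder who are admitted complete the BDI at every visit (Section 20). Unstable psychiatric conditions are excluded (Section 3.6, item 10). A suicide attempt or psychiatric hospitalization leads to withdrawal (Section 26). Section 1.2 reports no increase in depressive symptoms in an earlier trial among those with higher baseline depression scores. Site procedures and training material, which might settle the reading, are not in the documents.

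Most of this stands, and it makes the gap narrow. It does not close it. None of these provisions requires a suicidality assessment for a depressed-mood AE alone, and withdrawal after an attempt acts too late to serve as detection. It is also fair to say that *or* makes an isolated anxious-mood AE a mandatory trigger. That matches the asterisks, but the sponsor should confirm it.

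**Conclusion.** The concern holds as a minor point. The footnote admits two readings, the literal one is the less protective, and no other section decides between them. The likely intent is that either mood AE is enough, so this is probably a drafting slip.

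The practical size is unknown: the documents give no way to estimate how many participants would report one mood AE without the other, and they do not show that any staff apply the strict reading. The conclusion rests on the protocol text alone. It changes nothing in the primary endpoint, the analysis or which events are recorded as AEs.

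**What to change.** Confirm with the sponsor that either mood AE is meant to trigger the assessment. Then replace *and* with *or* between the two moods in the Section 21.1 footnote, so that a depressed-mood AE or an anxious-mood AE, each on its own, requires the Prime MD and a suicidality assessment. Send both sites a short note giving the corrected rule.

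The cost is one word in the protocol and the note. The downside is a few more short assessments with instruments the study already uses. If sites already read the footnote as either one, the change only records current practice.
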